5.2 Secondary endpoint definitions

- i. Red cell transfusion expressed as: (i) any vs. none; (ii) total number of units transfused;(iii) >4 units vs. ≤4 units⁴ occurring intra-operatively or during CICU stay (interval 2).
- ii. Non-routine pro-haemostatic treatments (see [section 5.1](#) for definition), occurring in interval 2, and expressed as: (i) any vs. none and (ii) total number of units or dose administered.
- iii. Serious post-operative complications, i.e. death, myocardial infarction (MI), any stroke, acute kidney injury (AKI) and sepsis during hospital admission.

Secondary endpoints i) and ii) will be extracted from INNOVIAN and will cover the period of CICU admission, with information on therapeutic protamine for the time interval 2b extracted from the CRFs (time from the post-operative sample to 12 hours post-CICU admission). Secondary endpoints detailed in iii) will be extracted from the PATS Database or INNOVIAN. Due to known limitations in the completeness of the PATS database for some of these data, INNOVIAN data will also be utilised to identify these outcomes; firstly by the event being recorded in INNOVIAN and secondly by an electronic review of the following five free text fields extracted from INNOVIAN:

- Intensivists Review
- Problems (Physician Daily Review and Plan)
- Progress note (Physician Daily Review and Plan)
- Surgical Review
- CICU Ward round
- Plan of care on discharge

The search terms to be used are as follows:

	Innovian search terms	Context terms
Death	n/a (all captured in PATS/NHS Strategic Tracing Service [NSTS])	
Myocardial Infarction	Myocardial infarction Infarct	Q wave MI/myocardial infarction Non-Q wave MI/myocardial infarction

³ In order to account for reoperations which were conducted due to surgical cause of bleeding, relevant electronic notes for all patients who required a reoperation will be reviewed by a cardiac surgeon (GJM). Any patient identification details will be masked. Those who, in the opinion of the surgeon, had a surgical cause of bleeding will be excluded from the definition of CCB.

⁴ RBC transfusion of 1-2 units may occur at any time during or after surgery, usually in response to low haematocrit for which bleeding is only one cause. Thus, the number of red cell units transfused reflects poorly the extent of bleeding. However, larger volume RBC transfusions (arbitrarily defined as >4 units) more reliably reflect clinically important bleeding.

STATISTICAL ANALYSIS PLAN

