COPTIC: Coagulation and platelet laboratory testing in cardiac surgery
A prognostic study of associations between post-operative test results
and subsequent bleeding

	MI STEMI NSTEMI ST elevation	Low cardiac output Cardiogenic shock IABP
Any stroke	Stroke Transient ischaemic attack, Hemiplegia Paralysis Paraplegia Dysphasia Cerebral/central nervous system (CNS) infarct/embolus	Loss of sensation CNS deficit Focal neurology Motor loss/deficit Sensation loss/deficit Brainstem Seizure Fit
Acute renal injury	Haemofiltration Haemodialysis Haemodiafiltration Dialysis Filtration Acute renal failure AKI Renal injury Kidney injury	New haemofiltration/dialysis CVVH RRT Already on dialysis
Sepsis	Chest infection Wound infection Mediastinitis Graft site infection Sternal wound infection Urinary tract infection Septic Sepsis Blood borne infection	Dehiscence Deep sternal wound Oozy sternum Positive blood culture Positive wound culture SIRS

Each of these secondary outcomes will be recorded as having occurred if there is evidence of a positive event within PATS or within INNOVIAN, including the review of free text.

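### The fixed free-text search list has short forms for infarction but none for transient ischaemic attack or urinary tract infection, so some stroke and infection events can be missed

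*SAP*

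**What the plan says.** SAP section 5.2 explains why a second source is used for the serious complications: "Due to known limitations in the completeness of the PATS database for some of these data, INNOVIAN data will also be utilised". Within INNOVIAN there are two routes, "firstly by the event being recorded in INNOVIAN and secondly by an electronic review" of free text. The strings for the free-text route are introduced by "The search terms to be used are as follows", with nothing that extends them to synonyms or abbreviations.

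The rows that matter here are:

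- **Infarction:** includes "MI STEMI NSTEMI ST elevation".
- **Stroke:** "Stroke Transient ischaemic attack, Hemiplegia Paralysis Paraplegia Dysphasia", followed by "Cerebral/central nervous system (CNS) infarct/embolus".
- **Sepsis:** chest infection and several wound terms, ending "Sternal wound infection Urinary tract infection Septic Sepsis Blood borne infection".

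A second column of context terms stands beside these. The SAP does not say whether a context term alone counts as a hit.

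Section 5.2 closes by recording an outcome when PATS or INNOVIAN, free text included, gives positive evidence of it. The same section announces an "electronic review of the following five free text fields" and then lists six.

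Section 6.2 names transient ischaemic attack in the stroke rule and urinary tract infection in the infection rule. For both variables the only sources are PATS and INNOVIAN.

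**The concern.** By listing MI, STEMI and NSTEMI, the authors show that they expect clinicians to abbreviate in these notes. The same allowance is not made for two conditions that the endpoint rules count by name. A string search for the full phrases does not return an entry that says only TIA or UTI. It does not return CVA or pneumonia either.

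Stroke and infection have no further source behind the search. In section 6.2, infarction also draws on death certificates, kidney injury comes from creatinine, and deaths are updated from a national tracing service. Because an event needs positive evidence, a missed one becomes a zero and not a missing value, so the missing-data rules in section 7.4.8 would not reveal it.

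At stake are the reported incidences of stroke and infection and the precision of the A4 models for them. If an outcome is rare, it could also fall below the minimum event count that section 7.4.3 sets for an analysis.

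**Working it through.** **1. Do the short forms match anything?** Each was compared, ignoring case, with all search and context terms in section 5.2, first as a whole word and then as a substring.

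| Entry in the notes | Whole-word match | Substring match |
|---|---|---|
| TIA | none | none |
| CVA | none | none |
| UTI | none | none |
| pneumonia | none | none |
| MI | yes | yes |
| NSTEMI | yes | yes |
| AKI | yes | yes |

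The only abbreviation in the stroke search terms is CNS, which qualifies infarct or embolus and is not a short form of stroke or transient ischaemic attack.

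**2. Are these defined events?** TIA and UTI abbreviate conditions named in section 6.2. CVA and pneumonia are not named there; they are synonyms that fall under stroke and chest infection.

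**3. When is an event lost?** All three conditions must hold:

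- PATS lacks it.
- INNOVIAN has not recorded it as an event.
- No other listed term, such as stroke, dysphasia, chest infection or sepsis, appears in that patient's searched notes.

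**4. What would a loss do?** The SAP gives no event rates, no figure for PATS completeness and no share of abbreviated entries. The missed fraction f is therefore purely an assumption, shown over a range, with misses unrelated to test results and no false positives.

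- Standard error factor for a rare outcome: 1/√(1 − f).
- True events needed to expect 11 observed, the smallest count that section 7.4.3 allows: 11/(1 − f), rounded up.
- Observed odds ratio: multiply both risks by (1 − f) and recompute. The true odds ratio is set at 2, with an assumed baseline risk of 2% or 10%.

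| f | SE factor | True events for 11 observed | OR at 2% | OR at 10% |
|---|---|---|---|---|
| 0.05 | 1.026 | 12 | 1.998 | 1.989 |
| 0.10 | 1.054 | 13 | 1.996 | 1.978 |
| 0.20 | 1.118 | 14 | 1.992 | 1.957 |
| 0.30 | 1.195 | 16 | 1.988 | 1.938 |

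One line in full, for f = 0.30 and baseline risk 10%: the exposed odds are 2 × 0.10/0.90 = 0.2222, so the risk is 0.1818. The observed risks are 0.07 and 0.1273, and the odds ratio is (0.1273/0.8727)/(0.07/0.93) = 1.938.

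**The case against.** The strongest reply is that the free-text search is the last of three routes. A patient with a stroke or an infection is likely to have several entries during the stay, and one listed word in any searched field is enough. Context terms such as focal neurology or SIRS might also bring up the notes. This stands as a limit on the size of the problem. It does not remove the problem, because the SAP leaves the role of the context terms open and nothing guarantees that a listed word appears.

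It is also fair to say that CVA and pneumonia are synonym gaps and contradict nothing in the plan. TIA and UTI are the firmer part.

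Two stronger readings are tempting, and the documents do not support them:

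- **Stroke and infection under-counted relative to kidney injury.** AKI is in the word list, but sections 5.3 and 6.2 derive that outcome from creatinine, so the list does not determine its count. The contrast with infarction remains.
- **A percentage for the loss.** A reader might multiply an assumed PATS shortfall by an assumed share of abbreviated entries: (1 − 0.8) × 0.3 = 6% up to (1 − 0.5) × 0.6 = 30%. None of these inputs is in the SAP. The product ignores events recorded in INNOVIAN outside the free text, and other listed terms in the same notes. It applies the gap to every infection, although wound infection, mediastinitis and sepsis are listed. It also counts events after CICU discharge, which notes limited to the CICU stay (section 4.1) would generally not contain.

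The five-versus-six slip is essentially clerical, since all six fields are named.

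**Conclusion.** The point holds as a minor gap in event capture. Followed as written, the list can miss transient ischaemic attacks and urinary tract infections that section 6.2 counts, as well as strokes and chest infections noted only as CVA or pneumonia. These patients would be scored as event-free.

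The size cannot be computed from the documents; the table shows only what an assumed loss would do. The effect falls on incidence and precision for two secondary outcomes. Odds ratios are little affected provided that misses are unrelated to the laboratory results, which is plausible because section 7.4 keeps those results from the treating clinicians. The minimum event count matters only for an outcome already close to it. Clinical concern about bleeding does not use this search and is unaffected.

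**What to change.** In the section 5.2 table, add TIA and CVA to the stroke search terms, and UTI and pneumonia to the sepsis search terms. Specify whole-word matching: as substrings, TIA would be found inside the word initial and UTI inside the word routine. Change five to six, so that every listed field is searched.

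It would help to report how many events were found only through the added terms, since that gives the size the SAP cannot. No change to the order of work is needed: section 4.2 already links INNOVIAN at Step 3, before the laboratory results at Steps 5 to 8.

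The cost is four strings and one corrected number, plus some extra false hits, such as an earlier TIA mentioned as history, to be checked within the electronic review already planned.

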5.3 Changes to the study objectives during the course of the study

These details differ slightly from those in the protocol (version 6, 21 March 2012):

STATISTICAL ANALYSIS PLAN

COPTIC: Coagulation and platelet laboratory testing in cardiac surgery
A prognostic study of associations between post-operative test results and subsequent bleeding

- In the protocol, all outcomes are defined as clinical outcomes, with no differentiation between primary and secondary outcomes.
- The definition of CCB detailed in the protocol includes the statement that the intervention took place before carrying out a Thromboelastogram (TEG) analysis, or requesting a TEG analysis. This has now been removed from the definition of CCB at the agreement of the clinical investigators (GJM and AM).
- Clinical decision to return to theatre because of suspected bleeding has been added to the definition of CCB.
- The interval defined for red cell transfusion was defined in the protocol as during hospital stay; these data are available for CICU admission only. No details were recorded in the protocol in relation to the early pro-haemostatic treatments; these data are also available for CICU admission only.
- The serious post-operative complications detailed in the protocol (secondary outcomes iii) were “death, myocardial infarction, permanent stroke, renal failure (new requirement for dialysis) and sepsis”. These have been amended to “death, myocardial infarction, **any stroke, acute kidney injury (AKI)** and sepsis”. AKI will be defined using a modified KDIGO AKI Work Group laboratory definition⁵; AKI is present if serum creatinine increases by $\geq 26.5 \mu\text{mol/l}$ from the pre-operative value within 48 hours of surgery OR serum creatinine increases ≥ 1.5 times the pre-operative value within 7 days of surgery. The decision to replace “renal failure (new requirement for dialysis)” with AKI using creatinine data was made in the light of the amount of missing information in PATS.

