6.2 Secondary endpoints

New variable	Rules	Data sources
RBC transfusion	Any RBC transfusion during interval 2	INNOVIAN clinical information

⁵ Diagnosis, evaluation, and management of acute kidney injury: a KDIGO summary (Part 1). Kellum *et al.* Critical Care 2013, 17:204

STATISTICAL ANALYSIS PLAN

COPTIC: Coagulation and platelet laboratory testing in cardiac surgery
A prognostic study of associations between post-operative test results and subsequent bleeding

New variable	Rules	Data sources
(binary)	(the time between post-operative samples are taken and discharge from CICU).	system
RBC >4 units (binary)	Any RBC transfusion >4 units during interval 2 (the time between post-operative samples are taken and discharge from CICU).	INNOVIAN clinical information system
Non-routine pro-haemostatic treatments (binary)	Any platelet, FFP, cryoprecipitate or rFVII transfusion during intervals 1 and 2 (the time between post-operative samples are taken and discharge from CICU), or therapeutic protamine during interval 2b (the time between post-operative samples are taken and 12 hours post CICU-admission).	INNOVIAN clinical information system and CRFs
Serious post-operative complications:		
Death (binary)	Vital status (alive vs. died in theatre OR died in hospital).	PATS Database (updated with NSTS data)
MI (binary)	Any MI occurring before discharge OR death from MI in hospital.	PATS Database, INNOVIAN clinical information system and death certificate data
Stroke (binary)	Any peri- OR post-operative neurological complication (stroke; transient ischaemic attack; hemiplegia; paralysis; paraplegia; dysphasia; cerebral/CNS infarct/embolus).	PATS Database, INNOVIAN clinical information system
AKI (binary)	Serum creatinine increased by ≥ 26.5 $\mu\text{mol/l}$ from the pre-operative value within 48 hours of surgery OR serum creatinine increased ≥ 1.5 times the pre-operative value within 7 days of surgery.	Creatinine data
Infection during hospital admission (binary)	Any infective complication (chest infection; wound infection; mediastinitis; graft site infection; sternal wound infection; urinary tract infection; septic; sepsis; blood borne infection).	PATS Database and INNOVIAN clinical information system

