7.4.3 Analysis models

All outcomes listed in the study protocol will be presented as per the template tables [Table T7 to T8](#). General methods of presentation are outlined below.

⁷ i.e. factors associated with the both the laboratory test result(s) (exposure) and the outcome, unbalanced across the groups and not an intermediary step in the causal pathway from the exposure to outcome

The primary outcome (CCB) and secondary outcomes (any RBC transfusions > 4 units RBC transfusion, non-routine pro-haemostatic treatments, death, MI, any stroke, renal failure, AKI and infections during hospital admission) are all binary data.

These binary outcomes will be presented as numbers and percentages of patients. The association between laboratory test results and outcome will be quantified using logistic regression for binary data. Estimates will be presented as unadjusted and adjusted odds ratios (OR) and 95% confidence intervals (95% CI). For these binary outcomes analyses will only be performed if more than ten patients in total experience the outcome.

The sensitivity and specificity of laboratory test results to predict the outcome will be described for different thresholds and laboratory tests will be compared using the area under the receiver operating characteristic (ROC) curve.

The association between time of withdrawal of P2Y₁₂ blocker and laboratory test results will be described using linear regression.

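### Section 5.2 counts AKI on any PATS or INNOVIAN evidence, against the creatinine-only definition in 5.3 and 6.2; pre-operative dialysis and a leftover renal failure outcome are also unresolved

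*SAP*

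**What the plan says.** **SAP 5.2, secondary endpoint definitions.** The third secondary endpoint is a set of serious complications: "death, myocardial infarction (MI), any stroke, acute kidney injury (AKI) and sepsis during hospital admission". On sources the section says "Secondary endpoints detailed in iii) will be extracted from the PATS Database or INNOVIAN"; creatinine results are not mentioned. The search-term table has a row for acute renal injury with terms such as dialysis, filtration and AKI. Its context terms include both new filtration or dialysis and "Already on dialysis". The section ends with a rule for the whole group: "Each of these secondary outcomes will be recorded as having occurred if there is evidence of a positive event within PATS or within INNOVIAN". That rule expressly takes in the free-text review.

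**SAP 5.3, changes to the objectives.** "AKI will be defined using a modified KDIGO AKI Work Group laboratory definition". The protocol's renal failure outcome, a new need for dialysis, was dropped in favour of AKI, and the decision to do so "using creatinine data was made in the light of the amount of missing information in PATS".

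**SAP 6.2, derivation of secondary endpoints.** AKI is present if creatinine rises by at least 26.5 µmol/l "from the pre-operative value within 48 hours of surgery OR serum creatinine increased" to at least 1.5 times the pre-operative value within 7 days. The data source column gives creatinine data and nothing else.

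**SAP 7.4.3, analysis models.** The list of binary secondary outcomes includes "any stroke, renal failure, AKI and infections during hospital admission", so renal failure and AKI appear as two separate outcomes.

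**The concern.** One endpoint has two current rules that use different sources. Section 5.2 looks for a recorded clinical event, in database fields or free text, at any time in the hospital admission. Sections 5.3 and 6.2 look for a laboratory change within 48 hours or 7 days. No text limits the closing sentence of 5.2 to the other complications or says which rule has precedence. Someone programming from 5.2 as written would build a different AKI variable from someone programming from 6.2.

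The variable matters because section 7 (analysis A4) plans association models and threshold-based prediction models for each secondary outcome. AKI status would be the dependent variable in those models. Section 7.4.3 also uses the event count to decide whether an outcome is modelled at all: more than ten patients must have it. An outcome with no derivation, which is the position of renal failure, cannot be put to that test.

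Existing dialysis is a separate classification problem. In a patient dialysed before surgery, a change in creatinine, or a note mentioning dialysis, need not mean a new injury.

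**Working it through.** No arithmetic applies. The SAP gives no AKI rate, event count or precision for this endpoint, so there is no figure to reproduce. The check is to set the sections side by side.

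**1. Does the 5.2 rule cover AKI?** Yes. AKI is named in endpoint iii, has its own row in the search table, and is not exempted from the closing sentence.

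**2. Does 6.2 merge the two rules?** No. In the 6.2 table the MI, stroke and infection rows each name PATS and INNOVIAN. The AKI row names creatinine data alone.

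**3. Where do the rules disagree?** Let

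- *a* = patients who meet the creatinine criterion with no PATS or INNOVIAN evidence;
- *b* = patients with PATS or INNOVIAN evidence who do not meet the creatinine criterion;
- *c* = patients with both.

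| Rule followed | AKI events |
|---|---|
| 6.2 (creatinine only) | *a* + *c* |
| 5.2 (PATS or INNOVIAN) | *b* + *c* |
| Either one | *a* + *b* + *c* |

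Between 5.2 and 6.2 the event count changes by (*a* + *c*) − (*b* + *c*) = *a* − *b*, while *a* + *b* patients change class. The count can therefore look stable while membership differs. The SAP gives none of *a*, *b* or *c*.

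**4. Which rule is intended?** Three places point the same way.

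- Section 5.3 states the laboratory definition and gives the reason for it, the amount of missing information in PATS.
- Section 6.2 repeats that definition as the derivation.
- Section 4.1 lists creatinine as a data source of its own, limited to the closest pre-operative result and results within 7 days after the operation. Section 4.2 builds baseline and post-operative creatinine datasets (Step 2) and links them (Step 4).

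The 7-day limit on the extract matches the 6.2 definition.

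**5. Are patients on dialysis before surgery dealt with?** Section 3 excludes only prisoners and people unable to consent, so these patients are eligible. Sections 5.3 and 6.2 do not mention them. Section 5.2 lists existing dialysis as a context term but does not say whether a hit excludes, counts or merely flags the patient. The only other use of dialysis status is in 6.4, for the pre-operative kidney function covariate. The information is therefore held but not applied to the outcome. Because dialysis status feeds that covariate, misclassification of these patients would be related to a baseline predictor.

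**6. Is renal failure a defined outcome?** No. Section 5.3 says AKI replaced it, 6.2 has no row for it, and 7.4.3 lists it beside AKI.

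**The case against.** The strongest reply is that the plan already shows its intention. A statistician who reads 5.3 and 6.2 together would use creatinine, and the AKI row in 5.2 is a remnant that was not trimmed. This stands, and it rules out presenting the matter as an open choice between two equal definitions. It does not remove the inconsistency, because the closing sentence of 5.2 is current text and still covers AKI.

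A reader might infer that the plan ignores existing dialysis altogether. The document does not support that: 5.2 names it as a context term, and the term may have been meant to screen out such hits. What is missing is a statement of how it changes the classification. The creatinine rule itself is silent.

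A reader might also want a share of AKI events at risk. Any such figure would need an assumed rate of disagreement and an assumed AKI incidence, and the SAP gives neither. The planned 2400 patients would also be the wrong base, since 3.6 restricts the analysis population to patients with assay, CRF, PATS and INNOVIAN data.

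Finally, it is tempting to argue that the creatinine rule misses patients filtered early, before creatinine rises. That is clinical reasoning the SAP does not contain. Letting the creatinine rule govern would not change it either, so it is not relied on here.

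**Conclusion.** The point holds as an inconsistency to be reconciled, in three parts.

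- The AKI row and closing sentence of 5.2 conflict with the creatinine-only definition in 5.3 and 6.2, which the rest of the plan shows to be the intended one.
- The creatinine rule applies without qualification to eligible patients already on dialysis, so it can record an event where there is no new injury.
- Renal failure survives in 7.4.3 as an outcome with no derivation.

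The size cannot be calculated from the document, and no percentage is offered. The reach is limited to one component of the third secondary outcome. CCB, and the platform comparison and Models 2A to 2E that are built on it, are unaffected. The conclusion assumes only that each section is current text, as the SAP presents it. It is worth correcting because these definitions determine the dependent variable of planned models and the correction costs almost nothing.

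**What to change.** 1. In 5.2, exempt AKI from the closing sentence and from the PATS or INNOVIAN source statement, and refer to 5.3 and 6.2, so that the creatinine definition alone governs AKI.
2. In 6.2, state that patients on dialysis before surgery are left out of the AKI analysis, identified from the dialysis information already used in 6.4. Report how many are left out.
3. In 7.4.3, either delete renal failure, or keep it as a separately named outcome with its own row in 6.2, derived from the acute renal injury search terms in 5.2. If it is kept, state that hits on existing dialysis are not counted.

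The cost is a few lines of SAP wording and one derivation condition, recorded in the amendment table. The AKI part needs no new data, since creatinine results and dialysis status are already held. The downside is that a few patients leave the AKI denominator.
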